4.2 Covariates Measured

At this time, planned covariates for the multivariate model include age and stage of fibrosis. For the model for which knowledge is the primary outcome, we will also control for health literacy. We will collect the following additional measures:

- **Clinical Characteristics:** We will document stage of kidney disease, stage of fibrosis, genotype of Hepatitis C, prior treatment history for Hepatitis C, time since Hepatitis C infection, and comorbidities.

[figure not shown]
- **Demographics:** We will explore whether any demographic variables (age, education, gender, race, insurance status) influence outcomes, controlling for significant covariates in the analysis.

- **Health Literacy:** We will control for health literacy in our analysis of the effect of our DA on knowledge. Participants will complete the Rapid Estimate of Adult Literacy in Medicine-Short Form [48].
- **Preferred Decision Role:** We will use The Control Preference Scale [49, 50] to assess the degree of involvement patients prefer in their medical decisions. Patients are asked to select one of five statements that best reflects their preference for decision control from active to collaborative to passive roles in treatment decision making.

4.3 Exploratory Analysis

- **Match between values and choice:** We will explore patients' values (as assessed in the decision tool by sliding a bar to indicate what is important to them) and their post-tool treatment choice for treating HCV and CKD, if they are leaning towards a choice. We will document whether their values match the choice they are selecting with their provider. This analysis will be completed after the tool and will be descriptive only, as we will not have a control group for comparison. However, it will be important to document their values and choice to indicate what percentage of patients who complete the tool select a treatment that matches their values. Future larger studies evaluating the tool could then explore the role of the decision tool in supporting patients to choose treatments aligned with their values.
- **Financial Toxicity:** We will ask patients about how much treatment costs (e.g., copayments, out-of-pocket costs prior to reaching deductibles) impact their choices using items from a financial toxicity measure previously developed in the context of cancer. We will explore whether patients leaning toward different choices report different levels of financial toxicity.

5 Study Flow Chart

6 STUDY PROCEDURES

6.1 Study Procedures

The Study Diagram in Section 5 summarizes the study procedures to be performed at each visit. Individual study procedures are described in detail below. It may be necessary to perform these procedures at unscheduled time points if deemed clinically necessary by the investigator. Furthermore, additional evaluations/testing may be deemed necessary by the Sponsor for reasons related to subject safety.

6.1.1 Administrative Procedures

6.1.1.1 Recruitment and Procedures

Aim 2- The goal of Aim 2 is to pilot test the DA to determine its efficacy and the likelihood of using it in routine practice. Eligible patients will be determined by the outpatient EMR (AllScripts). Once patients have been identified, their hepatologist or nephrologist will briefly describe the project and gauge patients' interest in participating. The project coordinator will then reach out to interested patients to describe the project in further detail and obtain informed consent. Patients will complete a brief pre-test questionnaire assessing socio-demographics, health literacy, knowledge, decisional conflict, and decision self-efficacy. All measures were chosen based on their short length so as not to burden participants. We have used a similar recruitment strategy and measures in past projects, and the procedures did not disrupt patient flow or introduce burden on patients [35, 36]. We will document CKD stage, dialysis status (yes/no), stage of fibrosis of the liver, whether or not the patient has tried using a DAA in the past to treat HCV, and presence of comorbidities (diabetes, heart disease, high blood pressure, HIV) to use for tailoring health information in the decision tool. This information will be collected from patients and clinicians and verified in the medical record with patients' consent.

Next, we will provide patients with the DA through tablet PCs on-site, brief training on how to use the tablets, and we will allow patients to view the DA. Patients can opt to view it on paper if they are uncomfortable with computers. They can take home a printed summary of the information to review at home before meeting with their clinician. The summary will also be placed in the patient's chart. After viewing the DA, patients will complete post-test measures of knowledge, decisional conflict, and decision self-efficacy. Recruitment will occur over 12 months. Patients will be provided with a \$20 gift card for participation and will have the added benefit of using the DA. We anticipate the pilot test to take about 30-45 minutes.

6.1.1.2 Informed Consent

Before subjects participate in the study, the project purpose and risks will be described by the research coordinator. Any questions participants have will be answered, and informed consent will be obtained. Informed consent will be obtained from each individual prior to their participation in the study. The consent form will cover the subjects most relevant to participants, including the purpose of the study, the institution conducting the research, sponsor of the study, length of the study, the risks and benefits of the study, and the confidentiality protections to be in

place. The research coordinator will ensure that subject understand that their participation is completely voluntary and that they can withdraw at any time without penalty. Participants will also be provided with the contact information of a research team member who can provide additional information about the study. We will ensure that the consent document states that this tool does not replace a conversation with a provider and is intended to be used to prepare patients for conversations with providers.

Consent will be documented by the participant's dated signature or legally acceptable representative's dated signature on an IRB-approved consent form, along with the dated signature of the person conducting the consent discussion. A copy of the signed and dated consent form will be given to the subject before participation in the study.

The initial informed consent form, any subsequent revised written informed consent form and any written information provided to the subject must receive the IRB/ERC's approval/favorable opinion in advance of use. The subject or his/her legally acceptable representative should be informed in a timely manner if new information becomes available that may be relevant to the subject's willingness to continue participation in the study. The communication of this information will be provided and documented via a revised consent form or addendum to the original consent form that captures the subject's dated signature or by the subject's legally acceptable representative's dated signature.

The informed consent will adhere to Washington University's Human Research Protection Office requirements, and will adhere to applicable laws and regulations and Sponsor requirements.

7 Safety Reporting and Related Procedures

Introduction

This is a primary data collection non-interventional study being conducted within routine medical practice. All direction for medication usage is at the discretion of a physician in accordance with usual medical practice. No administration of any therapeutic or prophylactic agent is required in this protocol, and there are no procedures required as part of this protocol.

7.1 Adverse Event Reporting

7.1.1 INVESTIGATOR RESPONSIBILITY

If the investigator becomes aware of any serious adverse event (SAE), including death due to any cause, or non-serious adverse reaction (NSAR) following the use of any Merck product, the event must be reported according to Table 1. The investigator must evaluate each SAE for causality and record causality on the AE form for each event reported.

Similarly, pre-specified Health Outcomes of Interest (HOIs) that meet criteria for SAE/NSAR, special situations, and any spontaneously reported AEs must be reported according to Table 1.

Table 1: AE Reporting Timeframes and Process for Investigators and Vendors

EVENT TYPE	INVESTIGATOR TIMEFRAME	VENDOR TIMEFRAME
	Investigator to Vendor [1], [2] OR Investigator to Merck [3]	Vendor to Merck [4]
SAE, regardless of causality (primary data collection) Serious pre-specified HOI Serious Special Situation, regardless of causality	24 hours from receipt	2 BD/3 CD from time of receipt from investigator
NSAR Non-Serious pre-specified HOI if NSAR Non-serious Special Situation, regardless of causality	10 CD from receipt	10 CD from time of receipt from investigator
Spontaneously reported adverse events for Merck products-submit using above timeframes		
If the investigator elects to submit AEs for non-Merck products , they should be reported to the market authorization holder (MAH) for that product or to the health authority according to the institution's policy or local laws and regulations. Note: Per [2], below, AEs for comparators must be entered in study database.		
Follow-up to any event-submit using above timeframes		

BD-Business Day; CD-Calendar Day

[1] AE reports from investigators must be transmitted via fax, secure email (if available), or entered directly into vendor's electronic data collection (EDC) platform, if utilized.

[2] **Investigator to Vendor:** Applies to events for **Merck study product, non-Merck comparators**, and ***other* Merck products** when a VENDOR is managing AE reporting from investigator to Merck. Events for **Merck study product** and **non-Merck comparators** are entered in study database for tabulation in study report. Events for ***other* Merck products** are *not entered in study database* but must be forwarded to Merck for regulatory reporting.

[3] **Investigator to Merck:** Applies to studies that do not have a vendor managing AEs.

[4] **Vendor to Merck:** Applies to events for **Merck study product** and ***other* Merck products** if the vendor is managing AE reporting between investigator and Merck. Not applicable for studies not using a vendor for AE reporting.

Submitting AE reports to Merck Global Safety: All AEs must be submitted to AER Mailbox [contact] (US), or toll-free [contact] (ex-US and US availability), in English using an AE form ([attached](#)) for reporting to worldwide regulatory agencies as appropriate.

7.2 DEFINITIONS

7.2.1 Adverse Event (AE)

Any untoward medical occurrence in a patient or clinical investigation subject administered sponsor's product and which does not necessarily have to have a causal relationship with this product. An adverse event can therefore be any unfavourable and unintended sign (including an abnormal laboratory finding, for example), symptom, or disease temporally associated with the use of the product, whether or not considered related to the product. Any worsening (i.e., any clinically significant adverse change in frequency and/or intensity) of a preexisting condition that is temporally associated with the use of the product, is also an adverse event.

7.2.2 Adverse Reaction (AR); also referred to as Adverse Drug Reaction (ADR)

An AE which has a causal relationship with the product, that is, a causal relationship between the product and the adverse event is at least a reasonable possibility.

7.2.3 Serious Adverse Event (SAE)/Serious Adverse Reaction (SAR)

An adverse event or adverse reaction that results in death, is life threatening, results in persistent or significant disability/incapacity, requires inpatient hospitalization, prolongation of existing inpatient hospitalization, is a congenital anomaly/birth defect, or is another important medical event. Other important medical events that may not result in death, may not be life-threatening, or may not require hospitalization may be considered an SAE/SAR when, based upon appropriate medical judgment, they may jeopardize the patient or subject and may require medical or surgical intervention to prevent one of the other outcomes listed previously. Examples of such medical events include allergic bronchospasm requiring intensive treatment in an emergency room or at home and blood dyscrasias or convulsions that do not result in inpatient hospitalization.

7.2.4 Non-serious Adverse Reaction (NSAR)

An adverse reaction that does not meet any of the serious criteria in 7.2.3.

7.2.5 Special Situations

The following special situations are considered important safety information and must be reported, regardless of seriousness or causality, if the investigator becomes aware of them:

- Overdose
- Exposure to product during pregnancy or lactation
- Lack of therapeutic effect
- Off-label use, medication error, misuse, abuse, or occupational exposure
- Suspected transmission via a medicinal product of an infectious agent

7.2.6 Health Outcome of Interest (HOI)

Health Outcomes of Interest (HOIs) are pre-specified clinical events or outcomes that are collected according to the protocol. HOIs may be represented as diagnosis, treatment or procedures. Examples of HOIs include syncope or hypoglycaemia collected as study endpoints. HOIs must be assessed as part of AE collection and may meet criteria for AE reporting. Specifically, the investigator must assess each HOI for serious criteria and causality. If the HOI meets criteria specified in the protocol for AE reporting, then it must be reported as such.

7.2.7 Sponsor's product

Sponsor's product includes any pharmaceutical product, biological product, device, diagnostic agent or protocol-specified procedure, whether investigational (including placebo or active comparator product) or marketed, manufactured by, licensed by, provided by or distributed by the Sponsor for human use.

7.2.8 Causality Assessment

A causality assessment is the determination of whether or not there is at least a reasonable possibility that a product caused the adverse event. Causality must be recorded on the AE form by the investigator for each reported event in relationship to a Sponsor's product.

Primary Data Collection

The assessment of causality is to be determined by an investigator who is a qualified healthcare professional according to his/her best clinical judgment. Use the following criteria as guidance (not all criteria must be present to be indicative of causality to a Sponsor's product): There is evidence of exposure to the Sponsor's product; the temporal sequence of the AE onset relative to the administration of the Sponsor's product is reasonable; the AE is more likely explained by the Sponsor's product than by another cause.

A qualified healthcare provider ([name] and/or [name]) will review the measures collected for any potential AEs. They will evaluate each SAE for causality and record causality on the AE form for each event reported.

8 Statistical Analysis Plan

8.1 Statistical Methods

Aim 2 Analytic Methods: For all analyses, descriptive statistics (e.g., frequencies, tendencies, variability) and diagnostic plots will be completed on all variables. Data will be examined for outliers and tested as appropriate for normality, linearity, and homoscedasticity. Appropriate corrective strategies, such as transformations, use of robust methods, or data reduction, will be used if problems are identified. These preliminary analyses are necessary to ensure high quality data and to test assumptions of the proposed models. We will also compare basic demographic and clinical characteristics between study enrollees and eligible refusers to characterize the representativeness of the included patients. We will also examine within group differences in our outcomes (knowledge, decisional conflict, decision self-efficacy) among patients pre- and post-use of the DA in a multivariable linear regression model controlling for up to 5 independent covariates (e.g. age, stage of fibrosis, health literacy). We intend to include knowledge, decisional conflict, and decision self-efficacy as primary outcomes in three separate multivariable models, age and stage of fibrosis as planned covariates in all models. Health literacy will be included as a covariate in the model with knowledge as an outcome. Others will be added if significant at the bivariate level. The knowledge scale that we develop will be pilot tested with patients as well. We will assess scale reliability using Cronbach’s alpha.

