We will make the DA available to complete via tablet PCs at the clinic to reduce bias in recruiting patients who are familiar with computers and the Internet. However, patients who want to see the information on paper can opt to do so given the age of this population and variations in comfort using computers. Patients will be able to review the DA content at any point, and can take home a printed summary of the information so that they can review a summary with caregivers and/or their clinician. The summary will also be placed in their medical chart so that the clinicians can use it to personalize discussions. We will work with our patient and clinician stakeholders to identify when the optimal timing will be for patients to complete this tool without disrupting clinic flow. We will conduct informal usability testing with 10 additional patients to ensure that wording and formatting is clear to patients. These patients will not be included in Aim 2 so as not to bias Aim 2 participants.

Aim 2 Methods: The goal of Aim 2 is to pilot test the DA to determine its efficacy and the likelihood of using it in routine practice. We will pilot this with 70 patients using a within subjects design. Outcomes will include change in decisional conflict, change in decision self-efficacy, change in knowledge about HCV treatment risks and benefits among patient with CKD, and the match between patients' intended choice and their preferences.

A quasi-experimental design was chosen to examine within group (pre-post use of the DA) outcomes. We considered conducting a randomized trial. However, randomizing individual patients or clinicians might lead to an underestimation of the effect of the DA, as the DA would likely contaminate standard procedures. Moreover, given the size and scope of this pilot project, our goal is to demonstrate feasibility and preliminary efficacy which can be accomplished at our institution through a within subjects design.

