8.1.1 Primary Objectives

For pilot testing of the tool in Aim 2, we will collect demographic information and measure decisional conflict, change in decision self-efficacy, change in knowledge about HCV treatment risks and benefits among patients with advanced CKD, DA usability, and the match between patients’ intended choice and their stated preferences.

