8.3 Sample Size and Power Calculations

Sample size and power were calculated using Power Analysis and Sample Size Software (PASS 11) [53]. We conducted our sample size calculation based on our expected change in decisional conflict based on past studies using DAs overall [54], and by consulting with the scale's user manual [55]. We expect a 15 point reduction in decisional conflict scores pre- and post- use of the DA and an effect size of 0.35. To examine within group differences in decisional conflict among patients pre- and post-use of the DA, we will conduct a paired-samples t-test. A sample size of 70 patients allows us to achieve a power of 80%, using two-sided t-test with a type I error of 5%.

We will also examine within group differences in our outcomes among patients pre- and post-use of the DA in a multivariable linear regression model controlling for up to 5 independent covariates (e.g. age, health literacy, race/ethnicity, decision role preference, clinical characteristics).

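### Do the differing labels for primary outcomes, and two analyses of decisional conflict with neither named as main, call for a change to the plan?

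*Combined protocol and SAP*

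**What the plan says.** Five places in the combined protocol and SAP bear on the point.

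- **8.1 Statistical Methods** names three outcomes: "We intend to include knowledge, decisional conflict, and decision self-efficacy as primary outcomes in three separate multivariable models". Age and fibrosis stage enter every model, and health literacy enters the knowledge model. Other covariates may be added if significant at the bivariate level.
- **8.1.1 Primary Objectives** lists what Aim 2 will collect: demographics, the same three outcomes, and then "DA usability, and the match between" choice and stated preferences.
- **4.3 Exploratory Analysis** covers that same match and says: "This analysis will be completed after the tool and will be descriptive only, as we will not have a control group for comparison".
- **4.2 Covariates Measured** also uses the term primary outcome: "For the model for which knowledge is the primary outcome, we will also control for health literacy".
- **8.3 Sample Size and Power Calculations** sizes the study on decisional conflict: "To examine within group differences in decisional conflict among patients pre- and post-use of the DA, we will conduct a paired-samples t-test". The power statement is "A sample size of 70 patients allows us to achieve a power of 80%, using two-sided t-test with a type I error of 5" per cent, with an expected effect size of 0.35. The next paragraph begins: "We will also examine within group differences in our outcomes among patients pre- and post-use of the DA in a multivariable linear regression model", with up to five covariates.

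Section 3.1 sets the ambition: "our goal is to demonstrate feasibility and preliminary efficacy". Section 8.2.3 repeats that results are to be read as preliminary.

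**The concern.** A reader who wants to know the main outcome and the main analysis gets no single answer. Section 8.1 calls three outcomes primary. Section 8.1.1 puts two further measures under a primary heading, and one of them is exploratory in 4.3. Decisional conflict has two analyses: the word primary goes with the regression, while the stated power belongs to the t-test.

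Two things could be at stake. First, a report could put forward whichever outcome or analysis looked best, and nobody could check that choice against the plan. Second, 8.1 does not say whether the regression uses change scores or separate pre and post records. If it dropped the pairing, the stated 80% power would not apply to it.

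**Working it through.** **1. The plan's own figure.** Inputs from 8.3: n = 70, effect 0.35 (read as SD-of-change units), two-sided 5%, paired t-test.

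- Noncentrality: 0.35 × √70 = 0.35 × 8.367 = 2.928, with 69 degrees of freedom and critical value 1.995.
- Power from the noncentral t: 82.3%. The smallest n for 80% is 67.

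So 70 patients give at least the stated 80%, with a small margin.

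**2. Does the power carry over to the regression?** Regress each patient's change on centred covariates. The intercept is then the mean change, with standard error (residual SD)/√70. If the covariates do not explain change, this is the paired t-test with slightly fewer degrees of freedom. In simulation (20,000 trials per setting, two covariates unrelated to change), power was:

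| Pre-post correlation | Paired t-test | Change-score regression | Pre and post rows, no patient term |
|---|---|---|---|
| 0.3 | 81.8% | 81.8% | 70.8% |
| 0.5 | 82.0% | 82.0% | 55.9% |
| 0.7 | 82.6% | 82.6% | 26.2% |

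If the covariates explain 10% or 30% of the variance of change, the regression's power rises to 84.7% or 89.3%.

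The last column can be checked by hand. Ignoring a pre-post correlation r makes the standard error too large by a factor 1/√(1 − r). Power is then about Φ(2.928 − 1.978/√(1 − r)), where 1.978 is the t critical value for about 136 degrees of freedom:

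- r = 0.3: Φ(2.928 − 2.364) = Φ(0.564) = 71%
- r = 0.5: Φ(2.928 − 2.797) = Φ(0.131) = 55%
- r = 0.7: Φ(2.928 − 3.611) = Φ(−0.683) = 25%

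This form is conservative: simulated rejection under the null was 2.0%, 0.6% and 0.03%. It would hide an effect, not create one.

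**3. Which form does the plan describe?** Section 3.1 defines the outcome as change in decisional conflict. Section 8.2.1 calls the design repeated measures and within subject. Sections 8.1 and 8.3 both speak of within-group differences before and after use of the aid. All of these point to an analysis that keeps the pairing. The unpaired column is an unlikely reading.

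**4. Do the labels change any analysis?**

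| Measure | Analysis given | Alternative in the text |
|---|---|---|
| Knowledge, self-efficacy | Adjusted pre-post model (8.1) | None |
| Decisional conflict | Paired t-test, then adjusted model (8.3) | Order only |
| Usability | Measured only after using the aid (4.1), so no pre-post model is possible | None |
| Values-choice match | Descriptive (4.3) | None; 8.1.1 gives no analysis |

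Section 8.3 never uses the word primary. It says which outcome was used for sizing, and sizing on one of several outcomes is not a contradiction. Section 8.1.1 is a list of what is collected, demographics included. In 4.2, primary outcome means the dependent variable of a model, and 8.1 can be read the same way.

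**The case for a change.** The strongest case for an edit is that the softer readings do not remove the ambiguity. If primary means only dependent variable, the plan names no primary outcome. If it means what it usually means, there are three and no decision rule. The adjusted model is also not fully fixed, because covariates may enter on bivariate significance. Its form matters too: testing the intercept with uncentred covariates would estimate change at age zero, with about 7% power in one illustration (age mean 58, SD 10, and fibrosis 0 to 4, all assumed). These data will inform a later randomized trial, and the edit would be wording only.

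The factual part stands: 8.1.1 and 4.3 label the match differently, and no main analysis is named. The consequences do not follow.

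- An analyst who reports mean change would not read it from an intercept at age zero, nor drop the pairing in a study built on it.
- Three independent tests at 5% carry a chance of 1 − 0.95³ = 14% of at least one false positive. That matters only if any one positive result counted as success, and the plan states no such rule.
- An unadjusted test followed by an adjusted model is ordinary practice, and 8.3 gives them in that order.
- Naming the paired t-test as the main analysis now could also be premature. Section 4.1 scores decisional conflict as four yes/no items, which sits awkwardly with the 15-point change in 8.3. That is a separate question and should be settled first.

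**Conclusion.** The inconsistency is real but is one of labels. Carried out as written, the plan yields a paired t-test on decisional conflict, three adjusted pre-post models, and descriptive results for usability and the values-choice match, all offered as preliminary evidence. None of these results changes with the reading of primary. The stated 80% power is sound for its test (82%) and carries over to a change-score regression (about 82%, or more if covariates explain change). With 70 patients, each mean change is estimated with a 95% confidence half-width of 1.995/8.367 = 0.24 SD of change, which is what a pilot needs to deliver.

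This rests on three assumptions: that 0.35 is in SD-of-change units, that the score can be treated as roughly continuous, and that the regression keeps the pairing the design calls for. It does not cover the mismatch between the 15-point change and the four-item score. The gap is one that analysts will fill sensibly, and no change to the plan follows.

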3.3 Inclusion Criteria

Aim 2 - Eligibility Criteria:

- Over the age of 18
- English-speaking
- Have HCV infection of any genotype
- And a diagnosis of CKD (we will stratify by GFR <30 and GFR >30).

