8.2 Bias

8.2.1 Methods to Minimize Bias

During the pilot phase (Aim 2), there is a chance of social desirability bias occurring. Social desirability bias is a type of response bias where participants give answers that are more favorable to the interviewer. We will reduce this bias by choosing the wording for our questions and materials carefully, using validated measures when available for Aim 2, assuring them there are no right or wrong answers, and reminding them that we are here to learn from them.

Confounding is often mentioned as a “mixing of effects” wherein the effects of the exposure under study on a given outcome are mixed in with the effects of an additional factor (or set of factors) resulting in a misrepresentation of the true relationship [61]. We controlled for confounding during study planning, where we specified our inclusion criteria and will control at the time of analysis by computing a multi-variable regression analysis.

We also selected a repeated measures/within subject design to minimize potential bias of a randomized trial randomizing at the patient level, where clinicians could contaminate the control group if they learned communication techniques after using the DA and applied them to controls as well.

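### Adding covariates by bivariate significance at n = 70 makes the reported covariate associations unreliable, and the confounding claim in section 8.2.1 can apply only to such between-patient associations

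*Combined protocol and SAP*

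**What the plan says.** Section 8.1 plans three multivariable linear models, one each for knowledge, decisional conflict and decision self-efficacy, with at most five covariates. Age and fibrosis stage are in every model, and health literacy is also in the knowledge model. For the remaining places the rule is "Others will be added if significant at the bivariate level". The section gives no significance level, no list of candidates, and no statement of whether the screen uses the pre, post or change score.

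Section 8.2.1 cites the inclusion criteria as control of confounding at the planning stage and adds that the investigators "will control at the time of analysis by computing a multi-variable regression analysis".

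Section 4.2 plans to explore whether five demographic variables "influence outcomes, controlling for significant covariates in the analysis". It also collects "stage of kidney disease, stage of fibrosis, genotype of Hepatitis C, prior treatment history for Hepatitis C, time since Hepatitis C infection, and comorbidities", health literacy and preferred decision role.

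The main contrast is within patients. Section 3.1 states: "Outcomes will include change in decisional conflict, change in decision self-efficacy, change in knowledge". Section 8.3 sizes the study on that contrast: "we will conduct a paired-samples t-test".

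**The concern.** There are two separate problems.

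First, a bivariate significance screen in 70 patients selects poorly. It admits some irrelevant covariates by chance and omits some real ones of modest strength. A covariate kept because it passed a test is then tested again on the same data, so its p-value is too small and its coefficient too large. These are the models named for the primary outcomes, and section 3.2 places the pilot ahead of a future randomized trial. A chance association could be carried forward as a sign of which patients gain most from the decision aid.

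Second, section 8.2.1 credits regression with controlling confounding without saying for which estimate. Age, fibrosis stage and literacy do not change between a pre-test and a post-test taken around one viewing of the tool (30-45 minutes in all, section 6.1.1.1). Adjusting for them cannot remove bias from the mean change. The real threat to that estimate is the learning effect acknowledged in section 8.2.3, which regression on these covariates does not address.

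**Working it through.** **The plan's own figure.** The plan gives no operating figure for the screen. Its only related figure is the sample size. For an effect size of 0.35 and two-sided 5%, an exact paired t-test needs 67 patients for 80% power, and 70 patients give 82.3%. The stated 70 is slightly conservative and does not bear on this point.

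**Inputs from the documents.** n = 70 (sections 3.1 and 8.3). Planned covariates: two in two models, three in the knowledge model (8.1). Cap of five (8.1), so two or three places are open. Unplanned variables in section 4.2: kidney stage, genotype, prior treatment, time since infection, comorbidities (counted once), education, gender, race, insurance and decision role. That makes 10 for knowledge, and 11 for the other two outcomes, where health literacy is not planned.

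**Assumptions, not in the documents.** Every one of these variables is screened, at 0.05; variables are normal; correlations between covariates are 0 or 0.3.

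**Step 1: the mean change.** Let D be post minus pre, regressed on mean-centred covariates. The least-squares intercept is mean(D) − Σ b_j × mean(centred x_j) = mean(D) − 0 = mean(D). The adjusted mean change equals the raw paired mean change whichever covariates enter; numerically the two differ by less than 1e-15. In simulation, its null rejection rate after screening was 5.2-5.5%, against 5.0% for the paired t-test.

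**Step 2: chance entry.** With k independent null candidates, P(at least one enters) = 1 − 0.95^k. For k = 10 this is 1 − 0.599 = 0.401; for k = 11 it is 1 − 0.569 = 0.431. Simulation with the cap applied gives the same for independent covariates and about 35-38% when covariates are correlated 0.3. The range per model is therefore 35-43%. The cap gives little protection: more candidates pass than there are places in only about 0.1-3% of null runs.

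**Step 3: what an entered noise covariate looks like.** Entry needs |r| ≥ t/√(t² + 68), where t is the 97.5% point on 68 degrees of freedom; this gives |r| ≥ 0.235. In the final model, entered null covariates have p<0.05 in about 77% of cases (independent) or about 48-53% (correlated 0.3); these rates move by a point or two between simulation runs. Per model, 22-37% of all-null runs end with a nominally significant screened-in covariate. Estimates are inflated too: a true correlation of 0.1 enters 13% of the time and then averages 0.29.

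**Step 4: real covariates missed.** By Fisher's z, entry probability is about Φ(atanh(r) × √67 − 1.96).
- r = 0.2: 0.2027 × 8.185 = 1.659; Φ(−0.301) = 0.382, so missed about 62% of the time.
- r = 0.3: 0.3095 × 8.185 = 2.534; Φ(0.574) = 0.717, so missed about 28% of the time.

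Because the threshold is unstated, the range is shown (independent candidates):

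| Screen | At least one chance entry, per model | Missed, r = 0.2 | Missed, r = 0.3 |
|---|---|---|---|
| 0.05 | 40-43% | 62% | 28% |
| 0.10 | 65-69% | 49% | 19% |
| 0.20 | 89-91% | 35% | about 10% |

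A looser screen trades missed covariates for more chance entries.

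**Step 5: does missing a confounder damage a prespecified demographic test?** A null demographic variable was simulated with correlation 0.3 or 0.5 with one confounder, itself correlated 0.2-0.4 with the outcome. Bias is per SD of the variable, in outcome SDs.

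| Adjustment | Bias | Type I error |
|---|---|---|
| None | 0.057 to 0.201 | 7.6-38.2% |
| Screened at 0.05 | 0.004 to 0.040 | 4.4-5.8% |
| Confounder fixed | −0.003 to 0.003 | 4.3-5.4% |

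A wider set of correlations (0.3-0.7 with the confounder) gave 5.1-6.3% with screening and 4.8-5.1% with the confounder fixed. The confounders that the screen misses are mostly those too weak to matter.

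**The case against.** The strongest reply is that little is at risk. The main covariates are already fixed, only two or three places are open, section 4.2 calls the demographic work exploratory, and section 8.2.3 limits Aim 2 to preliminary efficacy. Each model is more likely than not to admit no chance covariate, and the all-null setting, the 0.05 threshold and the candidate pool are assumptions. All of this stands, and it keeps the point minor. It does not rescue the rule, which is a stated selection procedure whose reported p-values do not mean what they appear to mean.

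A reader might infer more than the documents support:

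- *That the screen leaves the demographic tests seriously confounded.* Step 5 shows that it does not.
- *That fixing the list cuts the chance of a false finding from 81% to 30%.* The first figure is 1 − 0.95^32, counting bivariate entries over 10 + 11 + 11 = 32 tests. The second is 1 − 0.95^7, counting final-model tests of the 2 + 2 + 3 = 7 planned terms. These are different events. If education, gender, race and insurance are still examined for three outcomes, 12 tests are added and 1 − 0.95^19 = 62%.
- *That sections 8.1 and 8.3 conflict.* Section 8.3 offers "e.g. age, health literacy, race/ethnicity, decision role preference, clinical characteristics". Both lists are examples under the same cap, both include age and health literacy, and section 4.2 files fibrosis stage under clinical characteristics. They are compatible.
- *That kidney function is wrongly left to the screen.* Section 3.3 says "we will stratify by GFR <30 and GFR >30" without saying whether this concerns recruitment or analysis, so that reading is inference.

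**Conclusion.** The concern holds as a minor prespecification weakness with two parts. Under an assumed 0.05 screen of 10 to 11 null candidates, the rule admits at least one irrelevant covariate in 35-43% of runs per model. About half to three quarters of those admitted look significant in the final model, and modest real covariates are often missed. These figures depend on the assumed threshold, pool and correlations; Step 4 shows how they move with the threshold. The damage is confined to which covariates are reported as associated with the outcomes, and how strongly. It does not reach the mean pre-post change or the sample size, and it scarcely touches a prespecified demographic test.

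The second part needs no assumption about the screen. For the mean within-patient change, regression on characteristics fixed during the session controls no confounding, so the statement in section 8.2.1 has content only for between-patient associations.

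**What to change.** 1. In section 8.1, delete the bivariate rule. Fit the three models with the covariates already planned: age and fibrosis stage, plus health literacy for knowledge. Name any further covariate before analysis, on subject-matter grounds, within the existing cap of five.
2. In section 4.2, report the demographic and other covariate associations as exploratory, with 95% CIs and the number examined.
3. In section 8.2.1, limit the confounding statement to between-patient associations, and say that this regression does not address the learning effects noted in section 8.2.3.

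The cost is wording only, with no new data or patients. The downside is that a covariate suggested by the data can be reported only as exploratory.
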